## Study Overview

Study Overview	
Subjects	Recruit 60 subjects. Each subject will make 1-2 visits. The entire study is estimated to take approximately 6 months.
Inclusion/Exclusion Criteria	
Potential subjects will be given a checklist of the inclusion and exclusion criteria to determine if they are eligible to participate. A study staff will confirm the eligibility by the "yes" and "no" responses accordingly.
 
Inclusion Criteria (All answers should be yes):
 
 
• Between the ages of 5-17
 
• In good general health
 
• Fluent in English
 
• Parent or guardian willing and able to provide written informed consent
 
• Have 16 scorable teeth (non crown/bridge/or full amalgams)
 
• Have had a dental cleaning and exam in the past 24 months
 
 
Exclusion Criteria (To qualify, all answers must be no):
 
 
• Have advanced periodontal disease or severe gum disease
 
• Have mouth or teeth pain that prevents brushing in any areas
 
• Have intraoral piercings (tongue or lip) that cannot be removed
 
• Have non-controlled diabetes
 
• Have any autoimmune or infectious disease or any medical condition that would delay wound healing
 
• Have untreated visible cavities or untreated dental work
 
• Had oral or gum surgery in the previous 2 months
 
• Take antibiotic premedication for dental procedures
 
• Undergoing or require extensive dental or orthodontic treatment
 
• Current smoker
 
• Generalized recession over 1mm
 

Study Objectives	To compare plaque removal efficacy of an automated mouthpiece-based toothbrush to a manual toothbrush, and to assess effect on oral soft tissues.
Study Design	
 
• Single Site
 
• Parallel Design
 
• 60 Subjects stratified by dentition (primary, mixed, and permanent) are randomized evenly to 2 treatment groups
 
• Randomized, blinded, 2 treatment groups
 

Study Duration	
 
• 2 visits
 
• Each study visit will take approximately 90 minutes
 

Study Devices	
List of Devices:
 
Primary Investigation: (All 60 subjects)
 
 
1. Automated brush: 30 subjects
 
2. Manual toothbrush: 30 subjects
 

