## Background Information

A healthy mouth is a crucial condition for a healthy body.

Maintaining good oral health requires good oral hygiene meaning good plaque control. Plaque is one of the main etiological factors in dental decay and the principal etiologic factor for periodontal diseases which, beyond the discomfort they can inherently cause, are linked to more systemic conditions such as cardiovascular disease, pre-term low birthweight babies, Alzheimer's disease, and stroke.

It is now well recognized that tooth brushing is the most efficient plaque control method, at least when used in an optimal way.

Although toothbrushes have greatly evolved, from pig bristles to connected sonic devices, dexterity is still the key component to an efficient cleaning routine. Regardless of the type of toothbrush, if it cannot be used properly, plaque cannot be removed properly. And it has been shown in recent research that on a population with a general good health, the plaque score reduction is only an average 42% (range 30-53%) for manual toothbrushes and 46% (range 36-65%) for powered ones.

Based on these observations, the sponsor has developed a powered teeth cleaning device to bypass the variability of each individual dexterity according to which cleaning is performed by a contraction and a relaxation, according to successive cycles in the presence of a liquid dentifrice, of a mouthpiece made of a resilient material receiving and enclosing all the teeth of an arch.

---

[figure not shown]

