### **Statistical Analysis Plan**

Multiple sites within each subject will be evaluated using a Turesky Modification of the Quigley-Hein Plaque Index at the treatment visit both before and after brushing.

To assess the device effect after brushing, a paired t-test will be applied on the change outcome. An unpaired t-test will be used to compare the efficacy of both devices. A visual analog assessment will be done will be done on all subjects. The number and percentage of reactions related to each brushing method will be collected and the final tolerance score estimated.

The selection of 60 participants is expected to identify statistically significant differences in clinical parameters before and after brushing among the subjects of the study. The power analysis was based upon a recent study by Klonowicz et al in which a significant reduction of plaque was achieved after brushing of  $p<0.05$ .

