Study title: Efficacy of a Novel Brushing Device

NCT #: NCT05038293

PI Name: [name]

Document Name: Statistical Analysis Plan

Approval Date: May 14, 2021

Please find the attached statistical analysis used for this study.

Statistical Analysis Plan

The proposed clinical study is a Single-blinded, randomized controlled clinical trial in humans designed to assess compare the effects the test brushing device versus a manual toothbrush.

Primary outcome analysis plan: Oral health status and plaque accumulation was measured and obtained through clinical examination. The Turesky modification of the Quigley-Hein Index was used to quantify the amount of dental plaque on six assigned index tooth sites in children (ages 5-17; N=40) prior to and after use of the assigned oral hygiene device. Individual tooth plaque scores were then averaged within device group pre and post brushing and reported (mean \pm sd). Data was assessed for normality using the *rnorm()* function within the “stats” package within R Statistical Software. Difference in mean plaque data within and between device groups pre and post brushing was then evaluated using the parametric *t.test()* function and adjusted for multiple testing by False Discovery Rate (FDR) with an *alpha* of 0.05 (95% CI) using the “rstatix” package within R Statistical Software.

Secondary outcome analysis plan: Dentition status (primary, mixed, permanent) was recorded through clinical examination. Data from the primary outcome (Plaque score using the Turesky modification of the Quigley-Hein Index) was then stratified to determine the impact of dentition status on outcomes between device groups. Individual tooth plaque scores were stratified by Dentition status (primary: N = 2; mixed: N = 27; permanent: N = 11) and then averaged within device group pre and post brushing and reported (mean \pm sd). Difference in mean plaque data within and between device groups and by dentition status pre and post brushing was then evaluated using the parametric *t.test()* function and adjusted for multiple testing by False Discovery Rate (FDR) with an *alpha* of 0.05 (95% CI) using the “rstatix” package within R Statistical Software.

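### The primary between-device comparison is a covariate-free t-test on an unnamed plaque score; a child-level ANCOVA on the pre-brushing score would usually be more precise at almost no cost

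*SAP*

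**What the plan says.** The Study Overview of the protocol gives the objective as "To compare plaque removal efficacy of an automated mouthpiece-based toothbrush to a manual toothbrush", and Study Objectives and Purpose makes this between-device comparison primary. The protocol's Statistical Analysis Plan section has the plaque index scored before and after brushing. For the effect within a device, "a paired t-test will be applied on the change outcome". For the comparison between devices, "An unpaired t-test will be used to compare the efficacy of both devices".

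The SAP's primary outcome paragraph covers both in one sentence: "Difference in mean plaque data within and between device groups pre and post brushing was then evaluated using the parametric" t.test() function. The p-values are then "adjusted for multiple testing by False Discovery Rate (FDR") at 0.05, and the tests in that family are not listed.

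The Study Overview stratifies randomisation by dentition. In the SAP, dentition enters only the secondary analysis, where the plaque data are "stratified to determine the impact of dentition status on outcomes between device groups", with counts of "primary: N = 2; mixed: N = 27; permanent: N = 11". That analysis again uses t-tests.

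**The concern.** Two things are missing from the one test that answers the primary objective.

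- **No covariate.** The FDR step adjusts p-values. It does not adjust the comparison for anything measured on the child. The pre-brushing score is available for everyone and probably predicts the post-brushing score, and dentition was important enough to stratify on.
- **No named score.** The plaque index is named, but the quantity compared between arms is not. The protocol attaches change only to the paired test. Efficacy in the next sentence, and plaque removal in the objective, suggest change again. The Background describes brush performance as a percentage ("the plaque score reduction is only an average 42" per cent for manual brushes). The SAP wording could mean the pre-to-post difference, or separate between-group tests before and after brushing.

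At stake are the width of the interval for the device effect and what the primary p-value refers to. The SAP counts 40 children against a target of 60 in the protocol, so precision is not plentiful.

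**Working it through.** **The plan's own figure.** The target of 60 cannot be rebuilt. The protocol gives no effect size, SD or power, and its sample-size statement concerns differences before and after brushing, not between devices.

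**Inputs.** N = 40 is from the SAP. All else is assumed, because the documents are silent: 20 per arm, one mean score per child, normal scores, two-sided 0.05, and a true difference of 0.8 post-score SD. Let r be the within-arm pre/post correlation and k = SD_pre/SD_post.

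**Formulas.** Variance of the score in units of the post-score variance:

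- post score: 1
- change: 1 + k² − 2rk, which is 2(1 − r) when k = 1
- ANCOVA on the pre score: (1 − r²) × (N − 3)/(N − 4) = (1 − r²) × 37/36, the last factor being the price of estimating the slope

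Power comes from the noncentral t with noncentrality 0.8/√(2V/20) = 2.530/√V, on 38 df for the t-tests and 37 for ANCOVA.

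**Equal SDs (k = 1).**

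| r | V change | noncentrality | power | V ANCOVA | noncentrality | power | post-score power |
|---|---|---|---|---|---|---|---|
| 0.3 | 1.40 | 2.138 | 55% | 0.935 | 2.616 | 72% | 69% |
| 0.5 | 1.00 | 2.530 | 69% | 0.771 | 2.881 | 80% | 69% |
| 0.7 | 0.60 | 3.266 | 89% | 0.524 | 3.494 | 93% | 69% |

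The gain over change is 17/11/4 points, and over post score 3/11/23. ANCOVA beats both t-tests for r from about 0.17 to 0.94. At r = 0 it loses about 1 point to the post-score test (69.3% to 68.1%). In sample-size terms, 40 × V_ANCOVA/V_change = 26.7/30.8/34.9, so a change-score test on 40 children is about as precise as ANCOVA on 27/31/35.

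**Unequal SDs.** ANCOVA power is unchanged in these units; change-score power is not.

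| k | V change, r = 0.3/0.5/0.7 | change-score power | ANCOVA gain (unrounded powers) |
|---|---|---|---|
| 0.8 | 1.16/0.84/0.52 | 63/77/93% | about 9/3/0 points |
| 1.25 | 1.81/1.31/0.81 | 45/58/78% | about 27/22/14 points |

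**Percent reduction.** I simulated 20,000 trials per setting with a pre mean of 2.5, both SDs 0.5 and a 42% fall in the control arm. The 42% is the Background's average for manual brushes; the mean and SDs are assumed. For r = 0.3/0.5/0.7, the t-test on percent reduction has power 69/79/90% and ANCOVA 72/80/93%, a gain of about 1 to 3 points.

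**Other effect and sample sizes (k = 1).** At 0.5 SD with 20 per arm: change 26/34/51%, post 34%, ANCOVA 36/42/57%. At 0.8 SD with 30 per arm: change 73/86/98%, post 86%, ANCOVA 89/94/99%.

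**What ANCOVA does to the unnamed score.** With the pre score in the model, replacing the post score by pre minus post only reverses the sign of the device coefficient; its size, standard error and p-value are identical. That settles post score against absolute change. It does not cover percent reduction, which is not a linear function of the two scores.

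**Dentition.** In simulations with strata of 29 and 11 at r = 0.3, adding the stratum changed power by under 0.5 point when it explained nothing, and added roughly 2 to 3 points when it explained 10 to 20% of variance (assumed). The gain is minor.

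**The case against.** The strongest reply is that an unpaired t-test in a randomised trial is a legitimate choice, that change is the natural reading of the protocol, and that the size of the gain rests on quantities the documents do not give. Much of this stands. The change reading is the likelier one, so the large gains over a post-score test matter less. With k = 0.8 and r = 0.7 there is no gain over change at all, and on the percent-reduction reading it is small. What remains is that ANCOVA does about as well as, or better than, each t-test in nearly every setting, without knowing r or k in advance.

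A second reply is that the SAP is in the past tense and reports observed strata, so a new model may come after the results. That also stands. It limits the confirmatory value of ANCOVA, but not the need to say which score was tested.

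A reader might infer more than the documents support:

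- **That the planned test is biased.** It is not, if the child is the unit. The SAP describes averaging tooth scores by device group and never states one score per child, so validity is conditional. Nor does it say that teeth were tested as independent observations.
- **That the score was picked after seeing data.** If it had been, the chance that either the post or the change test is falsely significant would be about 9% in simulation. Nothing in the documents indicates that this happened.
- **That the FDR step inflates error.** It does not. Its cost depends on the unlisted family: none for two within-group tests plus one between-group change test, and about 4 points (69% to 65%) if between-group tests of both pre and post scores are included. Listing the family is a minor clarification.

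**Conclusion.** The point holds as one of precision and clarity. The primary between-device test uses no covariate and does not name its score, while a more precise analysis is available from data already collected. Under the assumptions above, with equal SDs, the gain over a change-score test is 17/11/4 power points at r = 0.3/0.5/0.7. It ranges from about nil to 27 points as the SD ratio runs from 0.8 to 1.25, and is about 1 to 3 points against percent reduction. The direction follows from algebra: before the small-sample term, change-score variance exceeds ANCOVA variance by (k − r)² and post-score variance exceeds it by r². The size is illustrative, because neither document gives r, the SDs or a target difference. All of it assumes one mean score per child, which the SAP should state.

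**What to change.** Make the primary between-device analysis a child-level ANCOVA: mean post-brushing score on device and mean pre-brushing score, with dentition stratum as a covariate. Pool the 2 primary-dentition children with the mixed stratum, since they cannot support a term of their own. State that each child contributes one mean score before and one after brushing. Report the adjusted difference with its 95% CI at two-sided 0.05, as the single primary test outside the FDR adjustment, and list the tests that remain in the FDR family. If percent reduction is wanted, name it as a separate secondary measure.

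If results are already known, label the ANCOVA and the pooling post hoc, show them beside the planned unadjusted t-test, and state which score that test used.

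The cost is a few sentences in the SAP, one regression on existing data and 2 degrees of freedom. If r is near 0, about 1 power point is lost to a post-score test.

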### **Number of Subjects:**

The target number of subjects to be randomized to this study are 60 subjects.

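### On its natural reading, the SAP t-tests the randomised arms before brushing and FDR-adjusts that test with the device comparison, costing about 2 to 5 points of power

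*SAP*

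**What the plan says.** The SAP's primary outcome paragraph first averages plaque scores within each device group before and after brushing. It then states: "Difference in mean plaque data within and between device groups pre and post brushing was then evaluated using the parametric" t-test function in R, with results "adjusted for multiple testing by False Discovery Rate (FDR) with an" alpha of 0.05. The secondary paragraph repeats this by dentition: "Difference in mean plaque data within and between device groups and by dentition status pre and post brushing was then evaluated". Neither paragraph lists the individual tests, says which of them form the FDR family, or names one primary contrast. Neither mentions a change score or a baseline covariate.

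The protocol is simpler. Under Study Overview, the children "are randomized evenly to 2 treatment groups". Its Statistical Analysis Plan section has a paired t-test on the change and one between-device test: "An unpaired t-test will be used to compare the efficacy of both devices". It has no pre-brushing comparison of the arms and no FDR step. The primary objective is to compare plaque removal between the device and a manual brush.

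**The concern.** The averaging sentence uses the pre/post phrase for two sets of means, one per time point. The testing sentence reuses the phrase for those same means. Read that way, the primary analysis holds four t-tests: pre against post in each arm (two), device against manual before brushing, and device against manual after brushing. One FDR statement covers them all.

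The third test is of no use. Allocation is random, so its null hypothesis is known to be true and rejection shows only chance. Inside an FDR family it is also not free. It takes up a place in the ranking, so the hurdle for the device comparison depends on a p-value unrelated to the devices. At stake are some power and a primary conclusion that, in a narrow range, the pre-brushing p-value can decide.

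**Working it through.** **Plan's own figure.** The protocol's sample size ("The target number of subjects to be randomized to this study are 60 subjects") is justified by before/after differences. It gives no effect size, SD or power, so it cannot be reproduced. For scale, at 80% power and two-sided 0.05 a two-sample t-test detects 0.74 SD with 30 per arm and 0.91 SD with 20 per arm.

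**Inputs from the documents.** Alpha 0.05; 1:1 allocation; 60 children in the protocol, 40 in the SAP ("six assigned index tooth sites in children (ages 5-17; N=40) prior to and after use of the assigned oral hygiene device").

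**Assumptions.** Benjamini-Hochberg; two-sided tests; one family of four; child-level scores; equal arms (20 or 30); equal SDs; between-device effects d in SD units; both within-device p-values near zero. The last is plausible after 24 hours without brushing and the 42% average manual reduction cited in the Background, but no SD is given.

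**Thresholds.** Benjamini-Hochberg compares the k-th smallest of m p-values with (k/m) × 0.05. The two within-device tests take ranks 1 and 2.
- Pre-brushing p > 0.05: the post-brushing test must pass at rank 3 of 4, so 3/4 × 0.05 = 0.0375.
- Pre-brushing p ≤ 0.05: the post-brushing test passes if its p ≤ 0.05, because all four then pass at rank 4.
- No pre-brushing test: rank 3 of 3, so 0.05.

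**Example, post-brushing p = 0.045.**
- Pre-brushing p = 0.40: adjusted p = 0.045 × 4/3 = 0.060, fails.
- Pre-brushing p = 0.03: adjusted p = 0.045 × 4/4 = 0.045, passes.
- No pre-brushing test: 0.045 × 3/3 = 0.045, passes.

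**Power.** Noncentral t with 2n − 2 degrees of freedom and noncentrality d√(n/2). For n = 20 and d = 0.8 this is 0.8 × √10 = 2.53.

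| n per arm | d | at 0.05 | at 0.0375 | loss (points) |
|---|---|---|---|---|
| 20 | 0.5 | 33.8% | 29.3% | 4.5 |
| 20 | 0.8 | 69.3% | 64.7% | 4.6 |
| 20 | 0.9 | 79.2% | 75.3% | 3.9 |
| 30 | 0.5 | 47.8% | 42.9% | 4.9 |
| 30 | 0.8 | 86.1% | 83.1% | 3.0 |
| 30 | 0.9 | 92.9% | 91.0% | 1.9 |

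Simulation of the full four-test procedure (pre/post correlation 0.3 or 0.7) agrees. The pre-brushing test changed the verdict in about 1% of null trials and 2% to 5% of trials with an effect. The null rejection rate was 3.7% to 3.9% with the test and 4.8% to 5.1% without it.

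**Sensitivity (20 per arm, d = 0.9).** If the manual arm showed no reduction (correlation 0.5), power is 69% with and 73% without the pre-brushing test. If the two between-device tests formed their own family, the threshold would usually be 1/2 × 0.05 = 0.025 and power would fall from 79% to 70%.

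**Baseline dependence outside the FDR step (20 per arm, correlation 0.7).** With no device effect and pre-brushing p ≤ 0.05, the post-brushing comparison rejects in 31% of trials, both under the four-test FDR rule and when tested alone. With d = 0.9, the unadjusted post-brushing t-test rejects in 99% of trials when imbalance favours the device by more than 1 SE and in 39% when it goes the other way. ANCOVA rejects in about 97% either way.

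**The case against.** **The text can be read otherwise.** The sentence might mean the pre-to-post difference, within and between devices. That would match the protocol and contain no baseline test. This stands as a possibility. The averaging sentence and the absence of any change score favour the time-point reading, but that remains an inference.

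**The effect is small.** This stands. In simulations with d of 0, 0.6 and 0.8, the case where a significant baseline p rescues a post-brushing p in the 0.0375 to 0.05 band arose in 0.07% to 0.23% of trials.

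**Deleting the test does not remove the main baseline dependence.** This also stands. It arises from comparing post-brushing scores without baseline adjustment, so deletion alone is an incomplete repair.

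**The within-device rejections are assumed.** True: the documents give no SD and no result for this device. If one within-device test failed, that test would itself tighten the hurdle. With within-device p-values of 0.000001 and 0.20 and no baseline test, a post-brushing p of 0.045 adjusts to 0.045 × 3/2 = 0.0675. This is a reason to take the primary contrast out of the family altogether.

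**Conclusion.** The point holds as a modest one. On the natural reading, an uninformative baseline test shares the FDR adjustment with the device comparison and usually lowers its threshold from 0.05 to 0.0375. Under the stated assumptions the harm is about 2 to 5 points of power and a verdict that an irrelevant p-value can decide within a narrow band. The secondary analysis repeats the wording. Its effect is not sized here, because with strata of 2, 27 and 11 children the within-device results cannot be taken for granted.

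A reader might infer two stronger things that the documents do not support:
- **That a chance imbalance makes a device difference too easy to declare.** The hurdle is looser when the arms differ at baseline than when they do not, but it never exceeds 0.05, because a Benjamini-Hochberg adjusted p is never below the raw p. The rule is conservative, not inflated.
- **That the FDR step makes the primary result hinge on baseline imbalance in general.** Outside the 0.0375 to 0.05 band it makes no difference. The broader dependence comes from the unadjusted post-brushing comparison.

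**What to change.** 1. Delete the pre-brushing between-device tests from the primary and secondary analyses. Report pre-brushing mean and SD by arm, and by dentition, without p-values.
2. Name one primary between-device contrast: the protocol's change score or, preferably, the post-brushing score adjusted for pre-brushing score and dentition stratum. In simulation (20 per arm, d = 0.9), power at correlation 0.3 and 0.7 was 65% and 95% for the change score, 82% and 97% for ANCOVA, and 79% at both for the unadjusted post score.
3. Test that contrast at two-sided 0.05 outside the FDR family. List the secondary tests to which FDR applies, and state the procedure.
4. Bring the SAP and the protocol's statistical section into line.

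The cost is revised wording and, if the analysis has been run, a re-analysis of existing data. No further children or measurements are needed. The SAP is written in the past tense and gives stratum counts. If results are already known, the change must be disclosed as made after the data were seen, with the results under the existing wording shown beside it. One downside is that within-device tests, if kept as secondary, no longer share in the primary claim.

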Study Summary	
Visit 1: Screening (may be by telephone)
 
 
• Inclusion / Exclusion reviewed
 
• Consent if in person visit
 
• Subject will be asked to abstain from brushing, flossing, gum or mouthwash for 24 hours prior to visit 2
 
• Schedule next visit
 
 
Visit 2:
 
 
• Consent
 
• Review Inclusion / Exclusion Questionnaire
 
• Randomization to experimental or control group
 
• Intraoral Evaluation by dental examiner
 
• Plaque disclosing and plaque score
 
• Intraoral photographs: (1 anterior, one posterior right and one posterior left)
 
• Brushing instructions
 
• Supervised and Timed Brushing with assigned product and measured toothpaste
 
• Restain with plaque disclosing solution and 2nd plaque index as well as gingival abrasion
 
• Intraoral photographs (1 anterior, one posterior right and one posterior left)
 
• Subject questionnaire
 

----------------------	--

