## **Study Objectives and Purpose:**

Primary Objective: To compare the effects of the test brushing device versus a manual brush on plaque removal

Secondary Objective: To determine if soft tissue abrasion differs between test and control group

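### The SAP's dentition t-tests do not test whether the device effect differs by dentition, and the protocol's abrasion objective has no specified between-arm test or estimate

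*SAP*

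**What the plan says.** **Dentition.** Under its secondary outcome analysis plan, the SAP says that the plaque data were "stratified to determine the impact of dentition status on outcomes between device groups". The counts are given as follows: "Individual tooth plaque scores were stratified by Dentition status (primary: N = 2; mixed: N = 27; permanent: N = 11". The method is then described: "Difference in mean plaque data within and between device groups and by dentition status pre and post brushing was then evaluated", using t-tests with an FDR adjustment at 0.05. No model, interaction term or contrast of device effects across strata is named. The FDR family is not defined.

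**Abrasion.** The protocol (Study Objectives and Purpose) lists one secondary objective: "Secondary Objective: To determine if soft tissue abrasion differs between test and control group". In the protocol's own Statistical Analysis Plan section, the unpaired t-test is assigned to efficacy. The nearest item to abrasion is this: "The number and percentage of reactions related to each brushing method will be collected and the final tolerance score estimated". The SAP's secondary outcome is dentition status, and abrasion does not appear in it. On collection, the Visit 2 summary in the Study Overview lists a second "plaque index as well as gingival abrasion" after restaining. The Schedule of Events has an intraoral examination before and after brushing, and Risk and Benefit Analysis says that the pre-brushing examination looks for abnormal abrasion or wounds. No index, scale or threshold is given.

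**The concern.** The dentition question is one of effect modification: is the test-minus-manual difference the same in each dentition group? Separate tests within strata of very different size do not answer it. One stratum reaching significance while another does not is weak evidence of differing effects, because the larger stratum simply has more power. FDR limits false discoveries among the tests that are run; it does not turn them into a test of a different hypothesis. At stake is a report that appears to show the device working in one dentition and not in another when the effects are identical.

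For abrasion, the objective is worded as a difference between groups, but nothing in either document commits to estimating that difference or its uncertainty. A stated objective could end as, at most, two descriptive counts.

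**Working it through.** **Plan's own figure.** 2 + 27 + 11 = 40, which matches the SAP's N = 40.

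**Primary dentition, child as unit.** A 1/1 split gives 1 + 1 − 2 = 0 degrees of freedom. A 2/0 split has no comparator. No between-device t-test exists either way.

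**Two readings of the t-tests.**
- Device tests within each stratum: each asks whether there is a device effect there, not whether the effects differ.
- Tests between dentition groups: these compare plaque levels, not device effects.

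Neither tests the interaction.

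**How often exactly one stratum is significant when the true effects are equal.** The stratum sizes come from the SAP. The rest is assumed: child-level analysis, splits 13/14 (mixed) and 5/6 (permanent), two-sided 0.05, and a common effect d in SD units. Power comes from the noncentral t with noncentrality d/√(1/n₁ + 1/n₂) and n₁ + n₂ − 2 df. At d = 0.8:
- Mixed: 0.8/√(1/13 + 1/14) = 2.08 on 25 df, power 0.515.
- Permanent: 0.8/√(1/5 + 1/6) = 1.32 on 9 df, power 0.219.
- Exactly one, unadjusted: 0.515 × 0.781 + 0.219 × 0.485 = 0.508.
- Exactly one, Benjamini-Hochberg (BH) over these two tests (smaller p ≤ 0.025, larger p > 0.05; power at 0.025 is 0.394 and 0.136): 0.394 × 0.781 + 0.136 × 0.485 = 0.374.

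| d | Unadjusted | BH, two tests |
|---|---|---|
| 0.5 | 30% | 19% |
| 0.8 | 51% | 37% |
| 1.0 | 58% | 47% |

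The family matters. By simulation at d = 0.8, adding two null pre-brushing tests gives 30–31%, adding four near-zero pre/post tests gives 47%, and adding both gives 44%. With splits 9/18 and 3/8 the result is 47–48% unadjusted and 33–35% with BH over two tests.

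**What an interaction term would deliver.** SE = SD × √(sum of 1/cell size); residual df = n − 5 (four cells and the baseline covariate); SD is the residual SD.

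| Cells (mixed; permanent) | SE | Detectable at 80% power | 95% CI half-width |
|---|---|---|---|
| 13, 14; 5, 6 | 0.72 | 2.07 SD | 1.46 SD |
| 9, 18; 3, 8 | 0.79 | 2.28 SD | 1.61 SD |
| 15, 14; 6, 5 (primary pooled with mixed) | 0.71 | 2.05 SD | 1.44 SD |

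With the primary-dentition children left out, power at a 0.8 SD difference in effects is 17–19%.

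**Abrasion.** No rate or scale is given, so only precision can be illustrated, at an assumed 20 per arm. Fisher's exact two-sided p is 0.106 for 0 vs 4 children and 0.047 for 0 vs 5. With none in either arm, the Newcombe 95% CI is ±z²/(20 + z²) = ±3.84/23.84, about ±16 percentage points.

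**The case against.** Several points on the other side are fair.

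- A reader might infer that the SAP intends to read one significant stratum as a subgroup effect. It never says so. The risk is a misreading that the plan leaves open, not a planned inference.
- A reader might infer that abrasion is not compared between arms at all, or not collected. The documents do not support either. Reactions are to be tabulated by brushing method, which would be a side-by-side description if they include abrasion; the protocol does not say whether they do. Taken together, the Risk and Benefit Analysis, the Schedule of Events and the Visit 2 summary suggest that abrasion is checked both before and after brushing. What is missing is a scale and a specified between-arm test or estimate.
- The percentages rest on an effect size, SD, splits and FDR family that the documents do not give. The direction holds across the variants tried; no single figure does.
- The SAP refers to individual tooth scores, so a reader might infer that teeth were analysed as independent units. The text leaves the unit open. A tooth-level test could return a p-value even in the stratum of two, but only by ignoring that teeth cluster within a child.
- The interaction model has little power. That is true, and it limits what the fix can claim, but stratum tests do not answer the question better.

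**Conclusion.** The point holds in two bounded parts.

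(a) The dentition analysis does not test its stated aim under either reading, and at child level it cannot compare devices in primary dentition. Discordant stratum results under equal effects are common: at 0.8 SD, 51% unadjusted and roughly 30–47% after FDR with the 13/14 and 5/6 splits. These figures assume child-level analysis and show scale only; they do not predict this trial's result.

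(b) The protocol's only secondary objective has no specified between-arm test or estimate, and the SAP omits it. This is a gap in analysis and in definition of the measure. It does not show that abrasion went unrecorded or that no description by arm was planned.

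Neither part bears on the overall device comparison for plaque.

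**What to change.** 1. **Dentition.** Replace the stratum t-tests with one child-level model of post-brushing plaque, adjusted for pre-brushing plaque, with device, dentition (mixed vs permanent) and their interaction. Report the interaction estimate with a 95% CI, labelled exploratory, and stratum estimates with CIs. Describe the two primary-dentition children only and leave them out of the interaction.
2. **Abrasion.** State how abrasion was recorded. From the existing records, report the between-arm difference in post-brushing abrasion (or abrasion new since the pre-brushing examination) with a 95% CI. Use Fisher's exact test if it is present/absent, or a rank-based comparison if it is graded or counted. If it was not recorded in a usable form, say that the secondary objective cannot be assessed.

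The SAP is written as the analysis already used. If that analysis is complete, report both items as supplementary.

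**Cost.** Two short analyses and some SAP wording, with no new visits. The stratum p-values are given up. The interaction remains imprecise, so the benefit is avoiding an unsupported subgroup claim rather than detecting a real one. At about 20 per arm, a null abrasion result must not be read as no difference.
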